regardless of relationship to study drug). From EOT or ET through EOS only AEs assessed as related to study drug by the PI (or designee) are to be reported. All SAEs that develop from the time of ICF signing until EOS (or ET if the subject discontinues from the study and does not complete a follow up call) are to be reported.

n: Glucose will be administered immediately following repaglinide dosing.

o: CCI

p: Subjects are confined to the CRU from C-I (Day -1, Period 1) through EOT (Period 2) or ET, including throughout the washout period.

Abbreviations: ♀ = Females, AE = Adverse events, BP = Blood pressure, C-I = Check-in, Chem = Chemistry, Coag = coagulation, ConMeds = Concomitant medication, CRU = Clinical research unit, ECG = Electrocardiogram, EOS = End of Study, EOT = End of Treatment, ET = Early termination, FSH = Follicle-stimulating hormone, Hem = Hematology, HIV = Human immunodeficiency virus, HR = Heart rate, ICF = Informed Consent Form, PI = Principal Investigator, PMP = Postmenopausal, Preg = Pregnancy, RR = Respiratory rate, Scr = Screening, T = Temperature, UA = Urinalysis.

6.2 Period 2

Study Procedures ^a	Study Days in Period 2 ^b													
	Days →		1											2
Hours →	0	0.25	0.5	0.75	1	1.5	2	3	4	6	8	12	0	12
Safety Evaluations														
Abbreviated Physical Exam ^c	X ^d													
12-Lead Safety ECG ^e	X ^d						X						X ^j	
Vital Signs (HR, BP, and RR) ^f	X ^d			X			X		X					X ^j
Hem, Serum Chem ^g , Coag, and UA	X ^d													
AE Monitoring ^h							X							
ConMeds Monitoring							X							
Study Drug Administration / Pharmacokinetic														
LOXO-292 Administration	X												X	X
Blood for LOXO-292 Pharmacokinetic ⁱ	CCI													
Other Procedures														
Confinement in the CRU							X							

Study Procedures ^a	Study Days in Period 2 ^b															
	Days →		3		4		5		6		7		8		9	
Hours →	0	12	0	12	0	12	0	12	0	12	0	12	0	12	0	12
Safety Evaluations																
Weight			X ^j													
12-Lead Safety ECG ^e	X ^j		X ^j		X ^j		X ^j		X ^j		X ^j		X ^j		X ^j	
Vital Signs (HR, BP, and RR) ^f	X ^j		X ^j		X ^j		X ^j		X ^j		X ^j		X ^j		X ^j	
Hem, Serum Chem ^g , Coag, and UA	X ^j						X ^j									
AE Monitoring ^h							X									
ConMeds Monitoring							X									
Study Drug Administration / Pharmacokinetic																
LOXO-292 Administration	X	X	X	X	X	X	X	X	X	X	X	X	X	X	X	
Blood for LOXO-292 Pharmacokinetics ⁱ	CCI															
Other Procedures																
Confinement in the CRU							X									

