13.2.6 Clinical Laboratory Tests

All tests listed below will be performed as outlined in the Study Events Flow Chart ([Section 6](#)). In addition, laboratory safety tests may be performed at various unscheduled time points, if deemed necessary by the PI or designee.

Hematology

- Hemoglobin
- Mean corpuscular hemoglobin concentration
- Mean corpuscular volume
- Hematocrit
- Red blood cell (RBC) count
- RBC distribution width
- Platelet count
- White blood cell/leukocyte (WBC) count
- WBC/leukocyte differential (absolute and percent):
 - Basophils
 - Eosinophils
 - Lymphocytes
 - Monocytes
 - Neutrophils

Coagulation

- Prothrombin Time/International normalized ratio
- Activated partial thromboplastin time

Serum Chemistry*

- Blood Urea Nitrogen
- Bilirubin (total and direct)
- Alkaline phosphatase
- AST
- ALT
- Uric acid
- Albumin
- Total protein
- Iron
- Calcium
- Sodium
- Potassium
- Magnesium
- Chloride
- Glucose (fasting)
- Creatinine**
- Cholesterol
- Triglycerides
- Phosphorus
- Creatine kinase
- Amylase
- Lipase

Urinalysis

- pH
- Color and appearance
- Specific gravity
- Protein***
- Glucose
- Ketones
- Bilirubin
- Blood***
- Nitrite***
- Urobilinogen
- Leukocyte esterase***

Additional Tests

- HIV test****
- HBsAg****
- HCV****
- Urine drug screen
 - Opiates
 - Opioids (methadone, oxycodone, and fentanyl)
 - Amphetamines
 - Barbiturates
 - Benzodiazepines
 - Cocaine metabolite
 - Cannabinoids
 - Phencyclidine
- Urine alcohol screen
- Cotinine
- Serum pregnancy test (for females only)
- FSH (for postmenopausal females only)****
- HbA1c
- Thyroid stimulating hormone****

* Samples for serum chemistry will be obtained following a fast of at least 12 hours at Screening and at Check-in (Day -1); at other scheduled times, serum chemistry tests will be performed after at least an 8 hour fast. However, in case of dropouts or rechecks, subjects may not have fasted for 12 or 8 hours prior to the time that the serum chemistry sample is being taken.

** At Screening and prior to dosing (Day -1 of Period 1), creatinine clearance will be calculated using the Cockcroft-Gault formula.

*** If urinalysis is positive for protein, blood, nitrite and/or leukocyte esterase, a microscopic examination (for red blood cells, white blood cells, bacteria, casts, and epithelial cells) will be performed.

**** Performed at Screening only.

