7. SAFETY

No inferential statistics are to be performed for the safety analysis.

All clinical safety and tolerability data will be listed by subject and assessment time points, including rechecks, unscheduled assessments, and early termination (ET), chronologically.

Continuous variables will be summarized using n, mean, SD, minimum, median, and maximum. Frequency counts will be reported for categorical data when appropriate.

The level of precision will be presented as follows: “n” as an integer, minimum/maximum in same precision as in the database, mean/median in one more precision level than minimum/maximum, and SD in one more precision level than mean/median.

Where individual data points are missing because of dropouts or other reasons, the data will be summarized based on reduced denominators.

When change from baseline is calculated, baseline is the last scheduled assessment before dosing at Period 1, including rechecks and unscheduled assessments, whichever is later, unless otherwise specified in the sections below. Rechecks, unscheduled assessments and ET measurements taken after first dosing will not be used in the summarization.

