For all laboratory values that are numeric, descriptive statistics (n, mean, SD, minimum, median, and maximum) will be presented for each laboratory test by treatment and time point. Change from baseline in Treatment B (defined below) will also be summarized. Postdose unscheduled events or rechecks will not be summarized. Similarly, ET results will not be included in summaries.

For each laboratory test, a shift table will be developed comparing the frequency of the results at baseline (above normal, normal, or below normal) to postdose results. For urinalysis tests, the categories are normal and outside normal.

Baseline is Day -1 of Treatment A (Period 1) and Day 1 predose of Treatment B (Period 2), and is the last non-missing predose measurement prior to dosing of LOXO-292, including rechecks and unscheduled assessments.

7.5 **Blood Glucose Monitoring**

Blood glucose monitoring will be performed at the following time points:

Table 7.5 Glucose Monitoring Time Points

Period	Period Day	Study Hour
1	Day 1	0*
1	Day 1	1
1	Day 1	2
1	Day 1	4
1	Day 1	6
1	Day 1	9
2	Day 10	0*
2	Day 10	0.5
2	Day 10	1
2	Day 10	1.5
2	Day 10	2
2	Day 10	3
2	Day 10	4
2	Day 10	6
2	Day 10	9
* performed prior dosing		

Descriptive statistics will be reported for blood glucose determinations and change from baseline by treatment and time point. Baseline is Day 1 predose of Treatment A (Period 1) and Day 10 predose of Treatment B (Period 2) and is the last non-missing predose measurement prior to dosing of repaglinide including rechecks and unscheduled assessments. Postdose rechecks, unscheduled assessments, and ET results will not be used for calculation of descriptive statistics. All blood glucose results will be listed by subject.

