7.6 Vital Signs (Blood Pressure, Pulse Rate, Respiration Rate, and Temperature)

Vital signs will be performed at the following time points:

Table 7.6 Vital Signs Time Points

Period	Period Day	Study Hour	Assessment
Screen	Screening		HR, BP, RR, T
1	Day -1	Check-in*	HR, BP, RR
1	Day 1	0**	HR, BP, RR, T
1	Day 1	0.75	HR, BP, RR
1	Day 1	2	HR, BP, RR
1	Day 1	4	HR, BP, RR
2	Day 1	0**	HR, BP, RR

Period	Period Day	Study Hour	Assessment
2	Day 1	0.75	HR, BP, RR
2	Day 1	2	HR, BP, RR
2	Day 1	4	HR, BP, RR
2	Day 2	0**	HR, BP, RR
2	Day 3	0**	HR, BP, RR
2	Day 4	0**	HR, BP, RR
2	Day 5	0**	HR, BP, RR
2	Day 6	0**	HR, BP, RR
2	Day 7	0**	HR, BP, RR
2	Day 8	0**	HR, BP, RR
2	Day 9	0**	HR, BP, RR
2	Day 10	0**	HR, BP, RR
2	Day 10	0.75	HR, BP, RR
2	Day 10	2	HR, BP, RR
2	Day 10	4	HR, BP, RR
2	Day 11	24***	HR, BP, RR, T

* performed within 24 hours prior dosing
 ** performed prior dosing
 *** performed at the end of Period 2 or prior to ET

Descriptive statistics will be reported for vital sign measurements (blood pressure, pulse, and respiration rate) and change from baseline by treatment and time point. Baseline is Day 1 predose of Treatment A (Period 1) and Day 1 predose of Treatment B (Period 2) and is the last non-missing predose measurement prior to dosing of repaglinide (Treatment A) or LOXO-292 (Treatment B), including rechecks and unscheduled assessments. Postdose rechecks, unscheduled assessments, and ET results will not be used for calculation of descriptive statistics. All vital signs results will be listed by subject.

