10. TABLE AND FIGURE SHELLS

The following table shells provide a framework for the display of data from this study. The shells may change due to unforeseen circumstances. These shells may not be reflective of every aspect of this study, but are intended to show the general layout of the tables and figures that will be presented and included in the final CSR. Unless otherwise noted, all in-text tables will be presented in Times New Roman font size 8 and post-text tables in Courier New size font 9. These tables will be generated according to the ADaM Model 2.1 and ADaM implementation guide 1.1.

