Programmer Note: All time points for a subject/test with at least one value deemed as CS by the PI will be presented in this table. If there were no CS values as deemed by PI (i.e., no "CS" or "Clinically Significant" in the PI flag or comment field in the laboratory dataset), then this table will contain only the statement: "There were no laboratory values deemed clinically significant by the PI in the study."

Note: \$ Age is calculated from the date of first dosing

H = Above Reference Range, L = Below Reference Range

Computer: N = Not Clinically Significant, Y = Clinically Significant

PI Interpretation: - = Not Clinically Significant, R = To be Rechecked, ^ = Will be Retested at a Later Event

Flag starting with "G" is graded according to NCI CTCAE grading.

Program : /CAXXXX/ECR/sas_prg/stsas/tab/PROGRAMNAME.sas DDMMYYYY HH:MM

Tables 14.3.5.1, 14.3.5.3, and 14.3.5.5 will have the following format.

Page 1 of X

Table 14.3.5.1 Clinical Laboratory Summary and Change from Baseline - Serum Chemistry (Safety Population)

Laboratory Test (unit)	Normal Range#	Time Point	Statistic	Treatment		Change From Baseline	
				A	B	A	B
Parameter1 (unit)	XX - XX	Day -1/1\$	n	XX	XX		
			Mean	XX.XX	XX.XX		
			SD	X.XXX	X.XXX		
			Minimum	XX.X	XX.X		
			Median	XX.XX	XX.XX		
			Maximum	XX.X	XX.X		
		Day 3	n		XX	XX	
			Mean		XX.XX	XX.XX	
			SD		X.XXX	X.XXX	
			Minimum		XX.X	XX.X	
			Median		XX.XX	XX.XX	
			Maximum		XX.X	XX.X	
		Day 6	n		XX	XX	
			Mean		XX.XX	XX.XX	
			SD		X.XXX	X.XXX	
			Minimum		XX.X	XX.X	
			Median		XX.XX	XX.XX	
			Maximum		XX.X	XX.X	

<Programmer note: Similar for remaining laboratory tests. Also need to add Days 10 and 11 time points of Period 2 (Treatment B). Sort alphabetically by lab test name.>

Note: # Lowest of the lower ranges and highest of the higher ranges are used. Refer to Appendix 16.1.10.1 for the breakdown.

\$ Day -1 for Treatment A (Period 1) and Day 1 for Treatment B (Period 2)

Baseline is Day 1 predose of Period 2 and is the last non-missing predose measurement prior to dosing of LOXO-292, including rechecks and unscheduled assessments.

Treatment A: <description>

Treatment B: <description>

Program: /CAXXXX/sas_prg/stsas/tab_PROGRAMNAME.sas DDMMMYYYY HH:MM

Tables 14.3.5.2, 14.3.5.4, and 14.3.5.6 will have the following format.

Page 1 of X

Table 14.3.5.2 Clinical Laboratory Shift from Baseline - Serum Chemistry (Safety Population)

Laboratory Test (units)	Treatment	Time Point	Baseline L			Baseline N			Baseline H		

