		Time Point	Measured Value	Change From Baseline	Time Point	Measured Value	Change From Baseline
Parameter1 (unit)	n	Day 1 Predose	XX		Day 1 Hour 0	XX	
	Mean		XX.XX			XX.XX	
	SD		X.XXX			X.XXX	
	Minimum		XX.X			XX.X	
	Median		XX.XX			XX.XX	
	Maximum		XX.X			XX.X	
	n	Day 1 Hour 0.75	XX	XX	Day 1 Hour 0.75	XX	XX
	Mean		XX.XX	XX.XX		XX.XX	XX.XX
	SD		X.XXX	X.XXX		X.XXX	X.XXX
	Minimum		XX.X	XX.X		XX.X	XX.X
	Median		XX.XX	XX.XX		XX.XX	XX.XX
	Maximum		XX.X	XX.X		XX.X	XX.X
	n	Day 1 Hour 2	XX	XX	Day 1 Hour 2	XX	XX
	Mean		XX.XX	XX.XX		XX.XX	XX.XX
	SD		X.XXX	X.XXX		X.XXX	X.XXX
	Minimum		XX.X	XX.X		XX.X	XX.X
	Median		XX.XX	XX.XX		XX.XX	XX.XX
	Maximum		XX.X	XX.X		XX.X	XX.X
	n	Day 1 Hour 4	XX	XX	Day 1 Hour 4	XX	XX
	Mean		XX.XX	XX.XX		XX.XX	XX.XX
	SD		X.XXX	X.XXX		X.XXX	X.XXX
	Minimum		XX.X	XX.X		XX.X	XX.X
	Median		XX.XX	XX.XX		XX.XX	XX.XX
	Maximum		XX.X	XX.X		XX.X	XX.X

CCI

Note: Baseline is Day -1 of Treatment A (Period 1) and Day 1 predose of Treatment B (Period 2) and is the last non-missing predose measurement prior to dosing of repaglinide (Treatment A) or LOXO-292 (Treatment B), including rechecks and unscheduled assessments.>

Treatment A: A single dose of 0.5 mg repaglinide administered at Hour 0 on Day 1

Treatment B: Multiple doses of 160 mg LOXO-292 (2 x 80 mg capsules) administered BID, approximately every 12 hours, for 10 consecutive days with 0.5 mg repaglinide coadministered on the morning of Day 10

Program: /CAXXXX/sas_prg/stsas/tab_PROGRAMNAME.sas DDMMMYYYY HH:MM

Table 14.3.5.9 12-Lead Electrocardiogram Summary and Change from Baseline (Safety Population)

ECG Parameter (unit)	Statistic	Treatment A			Treatment B		
		Time Point	Measured Value	Change From Baseline	Time Point	Measured Value	Change From Baseline
Parameter1 (unit)	n	Day Predose	XX		Day 1 Hour 0	XX	
	Mean		XX.XX			XX.XX	
	SD		X.XXX			X.XXX	
	Minimum		XX.X			XX.X	
	Median		XX.XX			XX.XX	
	Maximum		XX.X			XX.X	
	n	Day 1 Hour 2	XX	XX	Day 1 Hour 2	XX	XX
	Mean		XX.XX	XX.XX		XX.XX	XX.XX
	SD		X.XXX	X.XXX		X.XXX	X.XXX
	Minimum		XX.X	XX.X		XX.X	XX.X
	Median		XX.XX	XX.XX		XX.XX	XX.XX
	Maximum		XX.X	XX.X		XX.X	XX.X
				Day 2 Hour 0	XX	XX	
					XX.XX	XX.XX	
					X.XXX	X.XXX	
					XX.X	XX.X	
					XX.XX	XX.XX	
					XX.X	XX.X	

CCI

Note: Baseline is Day -1 of Treatment A (Period 1) and Day 1 predose of Treatment B (Period 2) and is the last non-missing predose measurement prior to dosing of Repaglinide (Treatment A) or LOXO-292 (Treatment B), including rechecks and unscheduled assessments.

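### Do the safety table shells, which name a Day -1 baseline and a Day 9 laboratory visit, put the safety summaries at risk?

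*SAP*

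**What the plan says.** **Baseline for vital signs and ECG.** SAP 7.6 states: "Baseline is Day 1 predose of Treatment A (Period 1) and Day 1 predose of Treatment B (Period 2"), and SAP 7.7 uses the same definition for ECG. Both add that baseline is the last non-missing reading before dosing. The general rule in SAP 7 leads to the same reading: "When change from baseline is calculated, baseline is the last scheduled assessment before dosing at Period 1". The footnotes under the shells for Tables 14.3.5.8 and 14.3.5.9 in SAP 10.3 instead open with "Baseline is Day -1 of Treatment A (Period 1) and Day 1 predose of Treatment B (Period 2) and is the last non-missing" predose measurement.

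**Laboratory days.** SAP Table 7.4 lists Period 2 laboratory tests on Days 1, 3, 6, 10 and 11. The protocol flow chart (section 6.2) marks the same days in the row "Hem, Serum Chem ^g , Coag, and UA", with Day 11 as the end-of-treatment visit and no mark on Day 9. The shift shell shared by Tables 14.3.5.2, 14.3.5.4 and 14.3.5.6 lists Days 3, 6, 9 and 11. The companion shell for the continuous laboratory summaries tells the programmer: "Also need to add Days 10 and 11 time points of Period 2 (Treatment B").

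**Status of the shells.** SAP 10 warns: "These shells may not be reflective of every aspect of this study". It adds that they are meant to show general layout and may change.

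**The concern.** A table programmer works from the shells, so a shell that disagrees with the text can turn into a wrong table. Vital signs and ECG are recorded both at Day -1 check-in and at Day 1 predose, so the choice of baseline reading affects every Treatment A change in those two tables. The footnote also contradicts itself: Day -1 cannot be the last predose reading when a later predose reading exists.

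The shift shell raises a different worry. Day 10 samples are drawn before the morning dose, so they are the last laboratory results on LOXO-292 without repaglinide. The second secondary objective asks about safety with and without repaglinide, and the protocol background lists raised liver tests and blood-count changes among the theoretical risks of LOXO-292. As drawn, the last shift shown on LOXO-292 alone would be Day 6.

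**Working it through.** The plan gives no figure to reproduce on this point. The check compares the places that define each item and then counts what a literal reading of the shells would touch.

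**1. Which Treatment A baseline does the SAP support for vital signs and ECG?**

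- SAP 7.6 and 7.7 (text): Day 1 predose.
- SAP 7 (general rule): the last scheduled assessment before Period 1 dosing. Tables 7.6 and 7.7 schedule an Hour 0 predose assessment on Day 1, so this is Day 1 predose.
- Second half of the footnote (last non-missing predose reading): also Day 1 predose. Day -1 would be used only for a subject whose Day 1 predose reading is missing, which is what SAP 7.6 and 7.7 imply too.
- Shell grid, Table 14.3.5.8: the first Treatment A row is Day 1 predose, with its change column blank. Changes begin at Hour 0.75, and no Day -1 row is drawn. If Day -1 were the baseline, the Day 1 predose row would carry a change of its own.
- Shell grid, Table 14.3.5.9: it also opens with a predose row and a blank change column, although the day number is not legible in the available text.
- First half of the footnote: Day -1. Nothing else in the SAP supports this for vital signs or ECG.

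The likely source is the laboratory sentence in SAP 7.4, "Baseline is Day -1 of Treatment A (Period 1) and Day 1 predose of Treatment B (Period 2"). Day -1 is correct there, because Period 1 has no later laboratory draw. Only the opening clause matches, however. The footnotes go on to name repaglinide for Treatment A and LOXO-292 for Treatment B, as SAP 7.6 and 7.7 do, while the laboratory sentence names LOXO-292 only. A copying slip is plausible but not proven. The glucose shell (Table 14.3.5.7) agrees with SAP 7.5, so the slip is confined to these two footnotes.

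**2. How much would a literal Day -1 baseline touch?**

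- Vital signs: 3 postdose times (0.75, 2 and 4 h) × 4 measures (systolic, diastolic, pulse, respiration) = 12 summary blocks.
- ECG: 1 postdose time (2 h) × 5 parameters (heart rate, PR, QRS, QT, QTcF) = 5 summary blocks.
- With the last-predose rule applied, both counts are 0.

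With 16 subjects these blocks rest on 12 × 16 = 192 and 5 × 16 = 80 individual changes, but the tables print summary statistics, so blocks are the relevant unit. The counts do not measure how far any mean would move. The flag for a QTcF change above 30 msec is specified in SAP 7.7, where the baseline is stated correctly. Treatment B baselines agree throughout.

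**3. Which laboratory days does the shift shell show?**

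- Scheduled after the Period 2 baseline: {3, 6, 10, 11}.
- Drawn in the shift shell: {3, 6, 9, 11}.
- Drawn but not scheduled: {9}. Scheduled but not drawn: {10}. Three of the four scheduled days match.

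For serum chemistry, protocol 13.2.6 has 22 list entries. Counting "Bilirubin (total and direct") as two gives 22 + 1 = 23 tests, so the shift table would lack 23 rows. The other two shift tables would likewise lose one row per test.

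**4. Would the slip survive, and what would be lost?**

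SAP 7.4 defines the shift tables as baseline against postdose results and excludes no day. It also keeps unscheduled postdose results out of the summaries, so a Day 9 row would be empty for every test while Day 10 data had no row to go into. Even if that went unnoticed, Day 10 values would still appear in the continuous summaries (Tables 14.3.5.1, 14.3.5.3 and 14.3.5.5) and the subject listings. Any outside the normal range would also appear in Tables 14.3.4.1 to 14.3.4.3.

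**The case for a change.** The best argument for correcting the SAP is that the caveat in SAP 10 does not excuse a known error. SAP 1 gives the shells a formal role in tracing outputs back to the data, so they are more than illustrations. The laboratory schedule was fixed when the shells were drawn, so this is not a late change. The shift shell has its own programmer note, which deals with urinalysis categories and says nothing about Day 10, while the companion shell does add the missing days. And even a programmer who uses the right baseline could leave the wrong footnote in the study report. The repair would be two footnotes and one row label.

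Much of this stands. The contradictions are on the page, the footnote could print wrongly if nobody edits it, and Day 10 is the more informative day for LOXO-292 alone. What does not follow is that the analysis is ambiguous or at risk. A programmer would have to overlook the section 7 text, the footnote's own last-predose rule and the table grid to compute the wrong baseline. To lose Day 10 from the shift tables, the programmer would have to overlook SAP Table 7.4 and accept an empty row. Some text next to the footnotes is blacked out and may hold further programmer notes, but the conclusion does not depend on it.

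**Conclusion.** The mismatches are genuine but clerical, and no change to the plan is called for. The statistical rules are stated correctly in SAP 7, 7.4, 7.6 and 7.7. The shells are declared to be general layout, and ordinary table programming and checking would settle both points from the existing text.

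The expected effect is nil. The worst case, a literal reading of both shells, is 12 vital-sign and 5 ECG change-from-baseline blocks computed from the wrong Treatment A reading, plus one missing time-point row per test in the three shift tables (23 rows for serum chemistry). These are descriptive safety outputs, and SAP 7 rules out inferential statistics on safety. The repaglinide comparison, the Treatment B safety baselines and the QTcF flags do not change, and no conclusion of the trial depends on the affected cells.

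This rests on two assumptions: that programmers follow the section 7 text where a shell conflicts with it, and that the Day 10 note in the companion shell is carried out so that Day 10 results appear in the continuous summaries.

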11. LISTING SHELLS

The following listing shells provide a framework for the display of data from this study. The shells may change due to unforeseen circumstances. These shells may not be reflective of every aspect of this study, but are intended to show the general layout of the listings that will be presented and included in the final CSR. These listings will be generated off of the Celerion SDTM Tabulation Model 1.4 mapped in accordance with SDTM Implementation Guide 3.2. All listings will be presented in Courier New size font 9.

Appendix 16.1.10.1 Clinical Laboratory Reference Ranges

Laboratory Group	Test Name	Sex	Age Category	Normal Range	Unit
Serum Chemistry	Test Name	XXXXXX	XX	XX - XX	units
	Test Name	XXXXXX	XX	XX - XX	units
	Test Name	XXXXXX	XX	XX - XX	units
	Test Name	XXXXXX	XX	XX - XX	units
	Test Name	XXXXXX	XX	XX - XX	units
	Test Name	XXXXXX	XX	XX - XX	units
Hematology	Test Name	XXXXXX	XX	XX - XX	units
	Test Name	XXXXXX	XX	XX - XX	units
	Test Name	XXXXXX	XX	XX - XX	units
	Test Name	XXXXXX	XX	XX - XX	units
	Test Name	XXXXXX	XX	XX - XX	units

<Programmer note: Sort alphabetically by lab test name within each lab group.>

<similar for remaining Laboratory Groups and Test Names>

Program: /CAXXXX/sas_prg/stsas/lis_PROGRAMNAME.sas DDMMMYYYY HH:MM

